# 8.3.2.3 EXPECTEDNESS

The PI, or his designee, will be responsible for determining whether an adverse event (AE) is expected or unexpected. An AE will be considered unexpected if the nature, severity, or frequency of the event is not consistent with the risk information previously described in Section 2.3.1, or if it is not known to be associated with any non-disqualifying underlying disease, disorder, or condition affecting the participant.

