## STATEMENT OF COMPLIANCE

The protocol, informed consent form(s), recruitment materials, and all participant materials will be submitted to the Institutional Review Board (IRB) for review and approval. Approval of both the protocol and the consent form will be obtained before any participant is enrolled. Any amendment to the protocol will require review and approval by the IRB before the changes are implemented to the study. In addition, all changes to the consent form will be IRB-approved; a determination will be made regarding whether a new consent needs to be obtained from participants who provided consent, using a previously approved consent form.

Investigators and clinical trial site staff responsible for study conduct, management, or oversight will complete Human Subjects Protection training in best practices for research.

1	PROTOCOL SUMI	MARY
1.1	SYNOPSIS	
Titl	e: dy Description:	How do the neck muscles influence head acceleration during sport- associated impact events in high school athletes? Sport-related concussion is a common injury associated with significant short- and long-term disability in high school athletes. This project will study up to 72 healthy male and female soccer athletes to determine how neck strengthening exercise affects head acceleration during sport- associated impacts (AIM 1) and define the mechanism relating neck strength and neck muscle volume to head acceleration under different impact conditions (AIM 2). The long term goal of this project is to optimize neck strengthening exercise programs to decrease the risk of concussion in high school athletes.

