## 2.3 RISK/BENEFIT ASSESSMENT

#### 2.3.1 KNOWN POTENTIAL RISKS

Potential risks associated with each component of the study include:

*Collection of demographic and historical information:* Loss of privacy and/or confidentiality is the main potential risk associated with this component of the study. This risk is considered non-serious. Likelihood: rare (< 1%).

*Collection of anthropometric data:* Subjects may feel embarrassed if they consider their height or weight to be outside of their self-perceived desirable range. There is also potential loss of privacy and/or confidentiality associated with anthropometric data collection. These risk are collectively considered non-serious. Likelihood: infrequent (1-10%).

*Cervical muscle volume (MRI) and cross sectional area (ultrasound) assessments:* There is no radiation exposure associated with either MRI or ultrasonography and there are no known adverse long term effects associated with either imaging modality. It is possible that subjects may feel uneasy while confined to the small space inside the MRI scanner. It is also possible that during sonographic assessment of the neck muscles the carotid baroreceptors could be stimulated by the transducer head resulting in a syncopal or near syncopal episode (fainting/near-fainting). These risks are considered nonserious. Likelihood: rare (< 1%). Not all subjects will undergo an MRI scan.

*Neck strength assessment:* Subjects may feel muscular discomfort associated with maximal isometric contraction of their cervical muscles. This risk is considered non-serious. Likelihood: infrequent (1-10%).

Assessment of the head's dynamic response to direct force application: Subjects may initially be concerned about how the direct force application loads will feel. This risk is considered non-serious. Likelihood: likely (10-25%). Subjects could potentially experience neck pain or a headache associated with this loading condition. The most likely etiology for neck pain is anticipated to be mild cervical muscle strain and the most likely etiology for headache is anticipated to be cervicogenic headache. The risk of developing neck pain or headache is considered non-serious. Likelihood: rare (< 1%). It is not expected that any more serious neck or neurological injury (concussion, radiculopathy, spinal cord injury, or vascular injury) will result from this procedure.

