*Kinematic measurements:* Light emitting diodes used with a high speed kinematic camera system may become hot to the touch when left to record continuously. Subjects could experience a minor superficial skin burn if a light emitting diode became too hot and was left in place, although this would be unlikely as the diodes are not affixed directly to the skin, but rather to a plastic plate surface affixed to the skin. The risk associated with this is considered non-serious. Likelihood: rare (< 1%).

*Skin preparation/application of skin adhesives:* Subjects may experience minor skin cuts or irritation associated with skin shaving or the adhesive backing on the surface EMG electrodes or other superficially adherent sensors. The risk associated with this is considered non-serious. Likelihood: infrequent (1-10%).

*Fitting of boil-and-bite mouth guards*: Subjects could receive minor burn to their hands or mouths while using boiling water to fit mouth guards to their mouth if direct contact with the boiling water occurred. The risk of burn is considered non-serious. Likelihood: rare (< 1%).

*Supervised exercise sessions:* Subjects are anticipated to experience delayed-onset muscle soreness following resistance training, which is a normal training-related phenomenon. The risk associated with this is considered non-serious. Likelihood: frequent (>25%). It is not expected that any serious training-related injuries will result from participation in study exercise sessions.

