## 8.3.4 ADVERSE EVENT REPORTING

AE and SAE reporting to IRBMED will occur per IRBMED standard reporting guidelines. Reporting to the DSMB will occur in conjunction with annual DSMB meetings as scheduled per the DSMB Charter. Additionally, any serious adverse event deemed possibly, probably, or definitely related to study procedures, or were IRBMED standard reporting guidelines otherwise necessitate more immediate reporting, will be reported to the DSMB on the same schedule as reports to IRBMED or within 14 calendar days of identification, whichever occurs first.

Note that if a series of related, expected AE's of moderate severity appear to be occurring at a frequency greater than previously known or expected, the study team will report this to IRBMED and the DSMB within 14 calendar days of identifying the trend.

Unrelated, non-serious AE's (expected or unexpected) will not be reported to IRBMED or the DSMB unless there appears to be a trend of events occurring at a frequency greater than previously known or expected, in which case the study team will also report this trend to IRB-MED as well as the DSMB within 14 calendar days of identifying the trend.

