## 8.4 UNANTICIPATED PROBLEMS

## 8.4.1 DEFINITION OF UNANTICIPATED PROBLEMS (UP)

The Office for Human Research Protections (OHRP) considers unanticipated problems involving risks to participants or others to include, in general, any incident, experience, or outcome that meets all of the following criteria:

- Unexpected in terms of nature, severity, or frequency given (a) the research procedures that are described in the protocol-related documents, such as the Institutional Review Board (IRB)approved research protocol and informed consent document; and (b) the characteristics of the participant population being studied;
- Related or possibly related to participation in the research ("possibly related" means there is a reasonable possibility that the incident, experience, or outcome may have been caused by the procedures involved in the research); and
- Suggests that the research places participants or others at a greater risk of harm (including physical, psychological, economic, or social harm) than was previously known or recognized.

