## 9.4.3 SAFETY ANALYSES

AEs and SAEs will be summarized by severity, relatedness, and expectedness using counts, with each AE counting only one time for a given participant, and will be presented in a table format.

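### Section 8.3.2.3 joins its two expectedness tests with *or*, so an adverse event that fits the listed risks still grades as unexpected in an athlete with no underlying condition

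*Combined protocol and SAP*

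**What the plan says.** Section 8.3.2.3 makes the PI or a designee responsible for grading expectedness and gives two tests. The first points back to the risks in Section 2.3.1: "An AE will be considered unexpected if the nature, severity, or frequency of the event is not consistent with the risk information previously described". The second follows directly: "or if it is not known to be associated with any non-disqualifying underlying disease, disorder, or condition affecting the participant". No other section redefines the term or limits the second test to participants who have a condition.

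The synopsis describes the population: "This project will study up to 72 healthy male and female soccer athletes". Section 2.3.1 lists procedural risks for these participants. For skin preparation and adhesives, rated infrequent (1-10%): "Subjects may experience minor skin cuts or irritation associated with skin shaving". For direct loading of the head, rated rare (<1%): "Subjects could potentially experience neck pain or a headache associated with this loading condition".

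Two later rules use the grade. Section 8.3.4 requires a report to IRBMED and the DSMB within 14 calendar days "if a series of related, expected AE's of moderate severity appear to be occurring" more often than previously known or expected. Section 9.4.3 sets out the safety table: "AEs and SAEs will be summarized by severity, relatedness, and expectedness using counts". In addition, Section 8.3.5 attaches 7-day and 14-day clocks to related, unexpected SAEs and states that the study has no related, expected SAEs.

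**The concern.** The usual purpose of an expectedness rule is to separate events that the described risks, or a known condition of the participant, already explain from events that neither explains. An event should count as expected if either source accounts for it, and the negation of that needs *and*. With *or*, an event is expected only if it both fits 2.3.1 and is linked to a condition the participant has. For an athlete without any such condition, the list in 2.3.1 then plays no part in the grade.

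What is at stake is safety reporting. One dimension of the safety table would stop discriminating among events in these athletes. Section 8.3.4 would also rest on a category that they cannot enter.

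**Working it through.** No arithmetic applies to the rule itself, and the plan states no figure to reproduce. The check is a truth table.

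Let A mean that the event is not consistent with 2.3.1 in nature, severity or frequency. Let B mean that the event is not known to be associated with an underlying condition of the participant. The rule as written is: unexpected = A or B. Hence expected = (not A) and (not B).

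| Event | A | B | As written (*or*) | With *and* |
|---|---|---|---|---|
| Fits 2.3.1, no linked condition | false | true | unexpected | expected |
| Fits 2.3.1, linked condition | false | false | expected | expected |
| Does not fit 2.3.1, linked condition | true | false | unexpected | expected |
| Does not fit 2.3.1, no linked condition | true | true | unexpected | unexpected |

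**First row.** Skin irritation from adhesives, occurring within the listed 1-10%, fits 2.3.1, so A is false. In an athlete with no underlying condition B is true, and the event is unexpected. B is true for every event in such an athlete, so the share of their AEs that can grade as expected is 0%. The share of athletes with no condition is not given, so this does not convert into a percentage for the trial.

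**Choice of example.** Neck pain or headache after direct loading is a weaker illustration. It is listed as <1%, and one case among 72 participants is 1/72 = 1.4%. Counted per participant, a single case could meet A on frequency alone. The plan does not say whether the denominator is participants or sessions.

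**The 8.3.4 trend rule.** As written, no AE in an athlete without a condition can be expected, so the related, expected class is empty for them. The other trend rule in 8.3.4 covers unrelated, non-serious AEs; none there names related, unexpected, non-serious AEs. Changing the connector does not settle this. A series judged more frequent than 2.3.1 describes makes A true through its frequency limb. In athletes with no condition B is also true, so the series is unexpected under *and* as well.

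**Third row.** Under *and*, an event that does not fit 2.3.1 but is linked to a participant's condition moves from unexpected to expected. If it were a related SAE, it would contradict the statement in 8.3.5 that there are none of that kind, and it would leave the 7-day or 14-day route. Section 8.3.4 would still send an SAE judged possibly, probably or definitely related to the DSMB on the IRBMED schedule or within 14 calendar days, whichever is first.

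**The case against.** The strongest reply is that this is a drafting slip with little practical effect. It over-calls unexpected, which is the cautious direction. The PI or designee makes the grade and may already apply the intended meaning. Delayed-onset muscle soreness, the one listed risk rated frequent, is not an AE under 8.3.1. As written, the slip shortens no SAE clock, because 8.3.5 foresees no related, expected SAEs. All of this stands and limits the weight of the point. It does not change the literal result in the first row of the table, or the fact that 9.4.3 tabulates the grade.

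A reader might also infer more than the documents support:

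- **A conflict with Section 8.4.1.** That section has similar wording ("Unexpected in terms of nature, severity, or frequency given (a) the research procedures"), but it defines a different term, the unanticipated problem. It also requires relatedness and a greater risk than was known. An over-labelled AE does not become an unanticipated problem.
- **Listed events passed on as new risk information.** Section 8.3.6 acts on new knowledge that may affect other participants, with DSMB input. The label alone does not trigger it.
- **Almost every AE in the trial graded unexpected.** The exclusions leave room for underlying conditions. For example, diagnosed migraine excludes only within the previous 3 years and concussion only within 6 months.
- **AEs already mis-graded.** The documents contain no AE log and no sign that the literal reading was applied.

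**Conclusion.** The point holds as a defect of wording in an operative definition. Under the text of 8.3.2.3, an AE fully consistent with 2.3.1 is unexpected in any athlete with no underlying condition. For those athletes 0% of AEs can grade as expected, the expectedness split in the 9.4.3 table is uninformative, and the related, expected class presupposed by 8.3.4 cannot arise. This rests on reading *or* literally and on some enrolled athletes having no underlying condition, which the synopsis makes likely but does not quantify. Correction is worthwhile, but it affects safety grading and reporting only; no endpoint, sample-size or efficacy analysis depends on it.

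**What to change.** In 8.3.2.3, replace the words that introduce the second test, *or if it is not known to be associated*, with *and it is not known to be associated*. An AE is then unexpected only when neither 2.3.1 nor a known condition accounts for it.

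In the same amendment:

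- Reconcile 8.3.2.3 with 8.3.5, so that no related SAE loses its expedited route because it is linked to a participant's condition, and so that the statement on related, expected SAEs remains true.
- Reconcile the frequency limb of 8.3.2.3 with the 8.3.4 trend rule, which asks for events that are expected and yet more frequent than expected.
- Check whether recorded AEs were graded on the literal reading, and re-grade only those that were.

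The cost is one changed connector, two cross-checks, a review of the AE log, and the IRB approval that the Statement of Compliance requires for any amendment. The downside is the shift in the third row of the table: events not listed in 2.3.1 but linked to a condition become expected. That is why the connector should not be changed without the 8.3.5 reconciliation.

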# 8.3.3 TIME PERIOD AND FREQUENCY FOR EVENT ASSESSMENT AND FOLLOW-UP

The occurrence of an adverse event (AE) or serious adverse event (SAE) may come to the attention of study personnel during study visits or if communicated to the study team between visits. The study team will not prompt participants for any specific solicited AE's, but will ask about unsolicited AE's at each study visit using the following general question: "Have you noticed any new illness, injury, or other health-related concerns since your last study visit?"

All AEs including local and systemic reactions not meeting the criteria for SAEs will be captured on the appropriate case report form (CRF). Information to be collected includes event description, time of onset, clinician's assessment of severity, relationship to study intervention (assessed by the PI or his designee with the training and authority to make a diagnosis), and date of resolution/stabilization of the event. All AEs occurring while on study must be documented appropriately regardless of relationship. All AEs will be followed to adequate resolution.

Any medical condition that is present at the time that the participant is screened will be considered as baseline and not reported as an AE. However, if the study participant's condition deteriorates at any time during the study, it will be recorded as an AE.

Changes in the severity of an AE will be documented to allow an assessment of the duration of the event at each level of severity to be performed. AEs characterized as intermittent require documentation of onset and duration of each episode.

The study coordinator or project manager will record all reportable events with start dates occurring any time after informed consent is obtained until 7 (for non-serious AEs) or 30 days (for SAEs) after the last day of study participation. At each study visit, the investigator will inquire about the occurrence of AE/SAEs since the last visit. Events will be followed for outcome information until resolution or stabilization.

## 8.3.4 ADVERSE EVENT REPORTING

AE and SAE reporting to IRBMED will occur per IRBMED standard reporting guidelines. Reporting to the DSMB will occur in conjunction with annual DSMB meetings as scheduled per the DSMB Charter. Additionally, any serious adverse event deemed possibly, probably, or definitely related to study procedures, or were IRBMED standard reporting guidelines otherwise necessitate more immediate reporting, will be reported to the DSMB on the same schedule as reports to IRBMED or within 14 calendar days of identification, whichever occurs first.

Note that if a series of related, expected AE's of moderate severity appear to be occurring at a frequency greater than previously known or expected, the study team will report this to IRBMED and the DSMB within 14 calendar days of identifying the trend.

Unrelated, non-serious AE's (expected or unexpected) will not be reported to IRBMED or the DSMB unless there appears to be a trend of events occurring at a frequency greater than previously known or expected, in which case the study team will also report this trend to IRB-MED as well as the DSMB within 14 calendar days of identifying the trend.

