#### 6.2 MEASURES TO MINIMIZE BIAS: RANDOMIZATION AND BLINDING

Subjects will be randomized using a centralized electronic randomization tool with equal allocation to the control and high-intensity neck strengthening groups. Balanced block randomization will be used to ensure equal sex and age category balance between the groups. Age category will correspond to high school under-class (i.e., age 13.0 - 16.49 years at the time of randomization) vs. upper-class (i.e., age 16.50 – 19.99 years) status given the typical maturation occurring in adolescents through the high school years. Subjects will be considered enrolled in the trial upon randomization and available data will be included in the intention to treat analysis. The Study Statistician, Strength Coach, Study Coordinator, and PI (or his Co-I designee when necessary to make a determination of AE relatedness to the study) will not be blinded to subject group allocation. Other members of the study team, including those responsible for performing the laboratory- and radiology-based assessment will be blinded to group allocation status. Subjects will not be informed of their group allocation status, although they will be aware of whether or not they are performing neck strengthening exercises during their exercise sessions. Subjects will be instructed not to discuss whether they are performing neck strengthening exercises during their exercise sessions.

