# 8.3.2.2 RELATIONSHIP TO STUDY INTERVENTION

All adverse events (AEs) will have their relationship to study intervention assessed by the PI, or his designee, based on temporal relationship and his/her clinical judgment. The degree of certainty about causality will be graded using the categories below. The study-assigned exercise program will always be considered suspect.

- **Definitely Related** There is clear evidence to suggest a causal relationship, and other possible contributing factors can be ruled out. The clinical event occurs in a plausible time relationship to study intervention administration and cannot be explained by concurrent disease or other exposure/event (e.gs., drug, chemical, toxin, pathogen, activity, environmental factor, traumatic event). The response to withdrawal of the study intervention (dechallenge) should be clinically plausible. If medically appropriate, a rechallenge procedure may be employed, with a positive response to rechallenge considered as confirmation of definite relatedness.
- **Probably Related** There is evidence to suggest a causal relationship, and the influence of other factors is unlikely. The clinical event occurs within a reasonable time after administration of the study intervention, is unlikely to be attributed to concurrent disease or other or other exposure/event, and follows a clinically reasonable response on withdrawal (dechallenge). Rechallenge information is not required to fulfill this definition.
- **Potentially Related** There is some evidence to suggest a causal relationship (e.g., the event occurred within a reasonable time after administration of the trial medication). However, other factors may have contributed to the event (e.g., the participant's clinical condition, other concomitant events). Although an AE may rate only as "possibly related" soon after discovery, it

can be flagged as requiring more information and later be upgraded to "probably related" or "definitely related", as appropriate.

- Unlikely to be related A clinical event whose temporal relationship to study intervention administration makes a causal relationship improbable (e.g., the event did not occur within a reasonable time after administration of the study intervention) and in which other disease or exposure/event provides plausible explanations (e.g., the participant's clinical condition, other concomitant treatments).

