# 8.3.5 SERIOUS ADVERSE EVENT REPORTING

Related, unexpected SAE's resulting in death or any life-threatening outcome will be reported to IRBMED and the DSMB within 7 calendar days of becoming aware of the event. Other related, unexpected SAE's will be reported to IRB-MED and the DSMB within 14 days of becoming aware of the event.

Unrelated, unexpected SAE's will be reported per standard IRBMED guidelines and in conjunction with regularly scheduled DSMB meetings.

Note, there are no related, expected SAE's associated with this study.

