## 10.1.5 SAFETY OVERSIGHT

Safety oversight will be under the direction of a Data and Safety Monitoring Board (DSMB) composed of 3 individuals with the appropriate expertise, including biostatistics, pediatric neurosurgery, and pediatric sports medicine. Members of the DSMB will be independent from the study conduct and free of conflict of interest. The DSMB will meet annually to assess safety and efficacy data on each arm of the study. The DMSB will operate under the rules of an approved charter that will be written and reviewed at the organizational meeting of the DSMB. At this time, each data element that the DSMB needs to assess will be clearly defined. The DSMB will provide its input to the PI and the National Institutes of Health Program Officer assigned to this project.

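### Section 8.3.4 keeps non-serious adverse events that an unblinded assessor calls unrelated out of routine DSMB reporting, so the by-arm safety review in 10.1.5 is incomplete

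*Combined protocol and SAP*

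**What the plan says.** Four parts of the protocol bear on this.

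- **What the DSMB is for.** Section 10.1.5: "The DSMB will meet annually to assess safety and efficacy data on each arm of the study". The same section leaves the list of data elements to a charter.
- **What it is sent.** Section 8.3.4 begins with a general rule: "Reporting to the DSMB will occur in conjunction with annual DSMB meetings as scheduled per the DSMB Charter". It then makes an exception: "Unrelated, non-serious AE's (expected or unexpected) will not be reported to IRBMED or the DSMB unless there appears to be a trend". The trend meant is a "trend of events occurring at a frequency greater than previously known or expected", which the study team reports within 14 calendar days of identifying it. Serious events are handled in Section 8.3.5: related, unexpected ones go to the DSMB within 7 or 14 days, and for the others, "Unrelated, unexpected SAE's will be reported per standard IRBMED guidelines and in conjunction with regularly scheduled DSMB meetings".
- **Who decides relatedness.** Section 8.3.2.2: adverse events "will have their relationship to study intervention assessed by the PI, or his designee, based on temporal relationship and his/her clinical judgment". Section 6.2 adds that the "PI (or his Co-I designee when necessary to make a determination of AE relatedness to the study) will not be blinded" to group allocation.
- **What is recorded.** Section 8.3.3 requires every adverse event on study to be documented whatever its relationship to the intervention. Section 9.4.3 plans counts by severity, relatedness and expectedness, and does not name arm as a classification.

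**The concern.** In a randomised trial the safety comparison that randomisation protects is all adverse events, by arm, without regard to cause. Once events are selected by an assessment of cause, and the assessor knows the arm, the counts that remain can differ between arms because of how events were classified. They can also agree between arms when the events themselves did not.

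Two routes are plausible here. First, only one arm does neck exercise. The same neck complaint may be somewhat more readily attributed to the programme in that arm than in the control arm, so more of the control background would drop out. Second, participants are soccer athletes. A non-serious injury or concussion sustained in a match has an obvious other cause and could be called unrelated in either arm. Such events would then be missing from the DSMB's routine data altogether, although concussion is the injury that the research programme aims to reduce.

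At stake is the quality of interim safety oversight while adolescents, many of them minors, are still being enrolled.

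**Working it through.** There is no planned figure to reproduce; the check is mainly of wording.

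**1. Is the sentence in 8.3.4 only about expedited reports?** Compare it with 8.3.5. For unrelated, unexpected serious events the protocol defers reporting to the scheduled DSMB meetings. For unrelated non-serious events it says that they are not reported, and names no later occasion. Where deferral is meant, the protocol says so. As written, the 8.3.4 rule is one of no reporting.

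**2. Is the filter aware of allocation?** Yes. Section 8.3.2.2 places the judgement with the PI or designee, and 6.2 states that both are unblinded, the designee expressly for the purpose of judging relatedness.

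**3. How wide is the filter?** Section 8.3.2.2 has five grades, the lowest two being unlikely to be related and not related. Section 8.3.4 does not say whether its term covers one of these or both.

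**4. Does the trend exception close the gap?** It is triggered by frequency relative to what is known or expected, not by a difference between arms. It has no threshold, and the study team applies it. Section 2.3.1 gives likelihoods for study procedures only, so events unrelated to the study have no stated reference frequency. When triggered, it calls for a report of the trend; it does not ask for counts by arm.

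**5. What does such a filter do to a comparison?** Let n₁ and n₀ be the true numbers of athletes with a given non-serious event in the neck and control arms, and a₁ and a₀ the proportions of those events judged related. The DSMB routinely sees n₁a₁ and n₀a₀, so

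ratio seen = (n₁/n₀) × (a₁/a₀).

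The true ratio is preserved only if a₁ = a₀ and both are above zero. The documents give none of the four quantities. The following only shows the range, and every rate except the last is an assumption. With equal allocation, 72/2 = 36 athletes per arm.

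| Assumed true risk, neck v control | Events per arm | Assumed share judged related | DSMB sees | Ratio |
|---|---|---|---|---|
| 15% v 15% | 36 × 0.15 = 5.4 v 5.4 | 50% v 50% | 2.7 v 2.7 | 1.0 |
| 15% v 15% | 5.4 v 5.4 | 60% v 40% | 3.2 v 2.2 | 1.5 |
| 15% v 15% | 5.4 v 5.4 | 80% v 20% | 4.3 v 1.1 | 4.0 |
| 25% v 10% | 9 v 3.6 | 0% v 0% | 0 v 0 | undefined |

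The only likelihood that the protocol gives for neck pain or headache is below 1% for the loading tasks (Section 2.3.1), and it covers procedure-related events only. At 1% there would be 36 × 0.01 = 0.36 events per arm, too few to show any pattern. The distortion therefore runs from none to large depending on inputs that nobody has.

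**The case against.** The case on the other side has real substance.

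- **The DSMB is not without data.** It receives related events at annual meetings, related unexpected serious events within 7 or 14 days, and unrelated unexpected serious events at scheduled meetings. Section 10.1.2 lets its members inspect all study documents and records. This stands, and it rules out the inference that the DSMB cannot compare the arms at all. The trend clause likewise rules out saying that every unrelated non-serious event is withheld. But a right to inspect does not put a table in front of the board.
- **The charter may require more.** It may; it is not among the documents. If it asks for all events by arm, it contradicts 8.3.4 as written, and the two need reconciling in any case.
- **Differential attribution may be modest.** A reader might infer that neck pain would be implausible, and so dismissed, in controls. The documents do not support that. Controls undergo the same head-loading, body-impact and heading tasks at all four assessments, for which 2.3.1 lists neck pain and headache as risks, and they train the shoulders, back and upper body (6.1.1). Section 8.3.2.2 also treats the exercise programme as always suspect and requires a documented alternative cause before an event is graded not related. These safeguards narrow the filter and make the 80% v 20% row an extreme. They do not remove it, and a match injury supplies exactly such a cause.
- **Final reporting is not filtered.** This stands: 9.4.3 applies no exclusion by relatedness, so the rule affects what the DSMB sees during the trial. The protocol also rates the study as no more than minimal risk, which limits the stakes. It does not justify an incomplete table when the data are already held.

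**Conclusion.** The point holds in a limited form. Followed as written, 8.3.4 leaves the DSMB's routine by-arm review under 10.1.5 incomplete for non-serious adverse events, because those judged unrelated by an unblinded assessor are left out unless the study team notices a trend against an expected frequency. The comparison that remains is open to attribution bias.

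Its size is unknown and cannot be derived from the documents, which give no event rates by arm or by relatedness; the table above shows direction and range only. It would be wrong to conclude that a false excess in the neck arm is likely, that a real one is being concealed, or that the DSMB has no by-arm safety comparison. The conclusion rests on reading 8.3.4 literally, which the contrast with 8.3.5 supports, and on the charter not already requiring a full table.

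**What to change.** 1. In 8.3.4, limit the exclusion of unrelated, non-serious adverse events to IRB reporting and to expedited (14-day) reporting.
2. In 8.3.4 and 10.1.5, consistently with the charter, state that each annual DSMB report tabulates all recorded adverse events by arm, giving both participants with at least one event and the number of events, regardless of relatedness or expectedness. Show relatedness as an added column, not as a condition for entry.

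This changes wording and one report. No new data are needed, since 8.3.3 already requires all events to be captured on the case report form. The cost is a longer annual table. Clinical management of participants is unaffected.
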